8.3.10 Blood sampling and safety laboratory evaluations

During the study, blood samples will be drawn for screening, safety and research purposes. The blood sampling schedule in the flowchart (section 8.3.17) shows the maximum amounts of blood that will be drawn. Following universal precautions, blood will be collected by venipuncture into vacutainer tubes. Blood specimens will be affixed with coded labels that link the specimen to the subject, specimen type, specimen collection date, and time-point. The cumulative blood draw for each subject over the entire course of study participation is maximally 500mL.

Biological safety parameters will be measured at the central laboratory of the RUMC. In the case where a laboratory assessment is outside the reference range, a decision regarding whether the result is of clinical significance or not shall be made by the investigator and shall be based, in part, upon the nature and degree of the observed abnormality. The assessment may first be repeated for confirmation. All abnormalities will be documented in the source documents, including clinical considerations.

Hemoglobin, hematocrit, red blood cell count, white blood cell count with differential (e.g. neutrophils, basophils, eosinophils, monocytes, lymphocytes) and platelet count will be measured at regular time points during the study. Alkaline phosphatase, total bilirubin, gamma-glutamyltransferase (γ GT), lactate dehydrogenase (LDH), alanine aminotransferase (ALT), aspartate aminotransferase (AST), sodium, potassium, creatinine and urea will be measured at regular time points during the study. Glucose, triglycerides and cholesterol will be measured only at screening.

8.3.11 Urine Toxicology analysis

A midstream urine sample (approx. 30ml) will be obtained, in order to avoid contamination with epithelial cells and sediments, to allow proper assessment. A toxicology screening will be performed at screening and at baseline. A positive test for amphetamines and cocaine is a reason for exclusion. A positive test for cannabis on the inclusion day prior to R0.6C administration will also be a reason for exclusion.

8.3.12 Pregnancy Test

A midstream urine sample will be obtained and assessed by commercially available hCG urine tests. This test will be done at screening and inclusion.

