5.2 Inclusion criteria

In order to be eligible to participate in this study, a subject must meet all of the following criteria:

1. Subject must sign written informed consent to participate in the trial.
2. Subject is a male or non-pregnant and non-lactating female age ≥ 18 and ≤ 55 years and in good health.
3. Subject is able to understand planned study procedures and demonstrate comprehension of the protocol procedures and knowledge of study by passing a quiz (assessment of understanding).
4. In the opinion of the investigator, the subject can and will comply with the requirements of the protocol.
5. Subjects are available to attend all study visits and are reachable by phone throughout the entire study period from day -1 until day 224 (end of study).
6. The subject will remain within reasonable travelling distance from the study center from day -1 until day 7 after each R0.6C administration and agrees not to travel to a malaria-endemic area during the study period
7. Subject agrees to their general practitioner (GP) being informed about participation in the study and agrees to sign a form to request the release by their GP, and medical specialist when necessary, of any relevant medical information concerning possible contra-indications for participation in the study to the investigator(s).
8. The subject agrees to refrain from blood donation to Sanquin or for other purposes throughout the study period according to current Sanquin guidelines.

9. Female subjects of non-childbearing potential may be enrolled in the study. Non-childbearing potential is defined as pre-menarche, current bilateral tubal ligation or occlusion, hysterectomy, bilateral ovariectomy or post-menopause. All subjects of childbearing potential must agree to use continuous adequate contraception* until 2 months after completion of the study. Female subjects must agree not to breastfeed from 30 days prior to R0.6C administration until 2 months after completion of the study. Female subjects must have a negative pregnancy test at the inclusion visit.

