	chills, nausea, gastrointestinal symptoms, headache, malaise, myalgia and arthralgia. No significant systemic adverse effects were observed in repeat dose animal toxicity studies.	symptomatic relief of any untoward side effects may be advised as necessary.
Study procedures		
Pain when taking blood samples	Because of the necessity to obtain frequent blood sampling for laboratory safety analysis, determining the concentration of R0.6C-specific antibodies, and measuring cellular immune responses, there is a risk of feeling faint, or experience mild pain, bruising, irritation or redness at the site where blood was taken. In rare cases arteries or nervous tissue may be injured or a punctured vessel may occlude and induce inflammation of the surrounding tissue.	Experienced and qualified medical personnel will draw blood. The amount of blood to be taken for sampling will not be harmful to the subject's health. Total blood volume taken over the whole study period will not exceed 500 mL.
Pregnancy risks		
Pregnancy and lactating females	Risks of the R0.6C vaccine to unborn babies are unknown at this time; pregnant females will be excluded from this study.	Females are only eligible for participation if they agree to use efficient contraception and the pregnancy test at the inclusion visit is negative. In case effective contraceptives are not available the clinical team may provide them. Volunteer who becomes pregnant during the trial will be withdrawn from any subsequent investigational product administration. Pregnant volunteers will not be withdrawn from the trial. Conditional on their agreement, they will be followed until the end of the pregnancy. Immunological and other exploratory blood samplings will be reduced to a minimum. Lactating females will be excluded from this study.
Risks to study personnel		

Needlestick injuries	The principal risk in the clinical setting is the handling of needles that may be contaminated with blood or body fluids and the associated risk of acquiring a blood-borne pathogen (including hepatitis B and C viruses and human immunodeficiency virus (HIV)).	Adherence to standard operating procedures (SOP) for working with infectious agents and universal precautions will reduce the risk of exposure. Subjects will be screened for hepatitis B and C and HIV prior to inclusion. Individuals positive for HIV, hepatitis B and C are excluded from the study.
-----------------------------	--	--

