8.3.6 Administration of R0.6C TBV candidate

Each enrolled subject will receive a total of four R0.6C vaccinations. The first vaccination will take place on day 0, the second on day 28 (+/- 3 days), the third on day 56 (+/- 3 days) and the last vaccination on day 168 (+/- 7 days). Subjects will be briefly assessed regarding any new medical events since the inclusion visit. The R0.6C vaccination will be prepared at bedside by study staff (nurse, study physician) or by the pharmacy according to the study arm; arms A will receive R0.6C with Alhydrogel alone, arms B will receive R0.6C with Alhydrogel and Matrix-M. R0.6C will be administered intramuscular in the deltoid muscle on alternating sides. The site of injection will be recorded on the case report form. Subjects will be observed for at least 1 hour after R0.6C administration. A list of solicited local and systemic symptoms will be reviewed after this observation period. If the occurrence of an adverse event or use of medication is confirmed by the study physician, it is recorded in the eCRF. After leaving the hospital, subjects will be asked to examine the site of infusion and record local signs and symptoms for seven days including bruising, erythema, swelling or induration. Subjects will be asked to record any AEs in the memory aid booklet (also see section 8.3.9).

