8.3.7 Follow up after R0.6C administration

Follow-up visits will be carried out on an outpatient basis at the study center. Subject will be asked to record local signs and symptoms in their memory aid booklet (also see section 8.3.9). The subject diary will be reviewed at each study visit and used as a base for discussion of possible local and systemic adverse events or medication use. In such cases, it may not be possible to obtain blood samples for non-safety endpoints.

If clinically significant (laboratory) abnormalities are identified during the study, subjects may be asked to return to the study site for further evaluation, including clinical evaluation and repeat laboratory testing as warranted. The trial physician can decide to initiate any additional diagnostics (including safety laboratory evaluations) at all times. For unexpected laboratory abnormalities, the laboratory test will be repeated.

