8.3.9 Patient reported outcomes (study diary)

At the inclusion visit, subjects will be issued symptom diaries. They will be asked to record all symptoms and medication use from the day of inclusion until end of study. Study staff will train subjects on use of memory aid booklets for self-assessment of solicited local and general adverse events through 7 days (day of R0.6C administration and subsequent 6 days) post- administration of R0.6C; and for self-assessment of adverse events and concomitant medications until day 84 after the last R0.6C administration.

The subject diary will be reviewed at each study visit and used as a basis for discussion of possible adverse events or medication use. If the occurrence of an adverse event or use of medication is confirmed by the study physician, it is recorded in the subject's EPD and eCRF. At the end of the study, the diary will be collected and kept as source data.

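### Pregnancy is tested only before dose 1, so an early, unrecognised pregnancy could be vaccinated at dose 2, 3 or 4

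*Protocol*

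**What the plan says.** Section 8.3.12 of the protocol limits the urine hCG test to two occasions: "This test will be done at screening and inclusion". The schedule in section 8.3.17 agrees, with two marks in the pregnancy-test row, at visits 1 and 2. Inclusion criterion 9 (section 5.2) is tied to the same moment: "Female subjects must have a negative pregnancy test at the inclusion visit". Under that criterion, women of childbearing potential "must agree to use continuous adequate contraception", up to two months beyond the end of the study.

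Table 5 (section 7.4.1) gives the reason for these precautions: "Risks of the R0.6C vaccine to unborn babies are unknown at this time". It then sets the rule for a pregnancy that arises later: "Volunteer who becomes pregnant during the trial will be withdrawn from any subsequent investigational product administration".

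Before a vaccination, section 8.3.6 provides this check: "Subjects will be briefly assessed regarding any new medical events since the inclusion visit". Section 8.3.9 adds a diary: "They will be asked to record all symptoms and medication use from the day of inclusion until end of study". Section 8.3.7 leaves further tests to judgement: "The trial physician can decide to initiate any additional diagnostics (including safety laboratory evaluations) at all times". The SAP does not mention pregnancy testing.

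**The concern.** The stop-dosing rule in Table 5 protects a fetus only if the pregnancy is known before the next injection. After the inclusion visit the protocol has no scheduled step that would detect a pregnancy the volunteer is unaware of. The questions at dosing and the diary depend on what she has noticed, and nothing prompts a discretionary test in a woman without symptoms.

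With every section followed to the letter, a first-in-human adjuvanted vaccine could therefore be given in early pregnancy at any of the last three doses. What is at stake is the safety of participant and fetus. The primary and secondary endpoints, the power calculation and the dose-escalation decisions are not affected.

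**Working it through.** The plan states no interval between test and dose, so there is no figure to reproduce. The check has two parts.

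**1. Interval from the last scheduled test to each dose**

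Inputs:
- Last scheduled test: the inclusion visit, labelled I1-1 in section 8.3.17, taken as day -1.
- Dose days and windows (section 8.3.6): day 0; day 28 ± 3; day 56 ± 3; day 168 ± 7.

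Formula: interval = dose day - (-1) = dose day + 1. The range comes from subtracting and adding the window.

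| Dose | Nominal interval (days) | Range with window (days) |
|---|---|---|
| 1 | 0 + 1 = 1 | 1 |
| 2 | 28 + 1 = 29 | 26 to 32 |
| 3 | 56 + 1 = 57 | 54 to 60 |
| 4 | 168 + 1 = 169 | 162 to 176 |

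So 3 of 4 doses have no scheduled test shortly before them.

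With tests at I2-1, I3-1 and I4-1 (nominal days 27, 55 and 167), the intervals become 28 - 27 = 1, 56 - 55 = 1 and 168 - 167 = 1 day. Using the window for a dose does not change this, because note 1 to section 8.3.17 moves the related visits along with the immunisation day.

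**2. What each existing safeguard can detect before doses 2 to 4**

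| Safeguard | Pregnancy the volunteer knows of | Pregnancy not yet noticed |
|---|---|---|
| Contraception (5.2) | Lowers the chance of conception; detects nothing | Same |
| Questions on new events (8.3.6) | Can reveal it | Not reliably |
| Diary review (8.3.9) | Can reveal it | Only if symptoms are recorded and prompt a test |
| Concomitant medication record (8.3.1, 8.3.17) | May help | May show that hormonal contraception was stopped, not that another method failed |
| Discretionary diagnostics (8.3.7) | Can confirm it | Permitted but not required |

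The Table 5 rule therefore works for recognised pregnancies. The right-hand column is the gap.

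**The case against.** The strongest objection is that the long intervals do not measure the hazard. A conception just after inclusion would be about 169 / 7 = 24 weeks old by dose 4, and would hardly be unnoticed. The window that matters is the few weeks before each dose, and it is about the same for doses 2, 3 and 4. This is right as far as it goes: 57 and 169 days show how long the plan goes without a test, and should not be read as a risk that grows with time. The point needs only that some early pregnancies in each of those windows would be missed.

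The expected number of cases is also likely to be small. As an illustration on assumed inputs, take 16 women of childbearing potential, 1% to 15% pregnancies per woman-year, and 1 to 3 weeks before each of three doses in which a pregnancy is detectable but unnoticed (3 to 9 weeks in all). The expected number of exposures is then between 16 × 0.01 × 3/52 = 0.01 and 16 × 0.15 × 9/52 = 0.4 for the whole trial. None of these inputs comes from the documents. Even so, the result would be well below one case but not zero, and section 5.2 accepts barrier methods, which depend on continued correct use.

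A third argument is that there is no contradiction: Table 5 promises contraception, a negative test at inclusion and no further doses after pregnancy, and the protocol delivers exactly that. This also stands. The point is a weakness in a chosen design, not an inconsistency. But the sponsor did not regard contraception alone as enough for dose 1, where it tests twice, and the same reasoning applies to later doses.

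Finally, the vaccine is a non-replicating protein, and the repeat-dose rabbit study showed no systemic toxicity. That is some reassurance, but the preclinical summary (Table 2) lists no reproductive or developmental toxicity study, and the protocol itself calls the fetal risk unknown.

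**Conclusion.** The concern holds and should be fixed. Section 8.3.12 schedules pregnancy tests only before dose 1, and no other section requires one before doses 2, 3 or 4. An early, unrecognised pregnancy could be vaccinated at any of those doses without a protocol deviation.

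The size that can be stated is the gap in coverage set out above. It rests on the inclusion visit taking place on day -1, as the schedule labels it. The number of pregnancies likely to be exposed cannot be derived from the documents. With mandatory contraception it is probably very small, but the possible harm falls on a fetus, its extent is declared unknown, and the remedy is inexpensive.

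**What to change.** In section 8.3.12, add the same urine hCG test at I2-1, I3-1 and I4-1 for women of childbearing potential, and require a negative result before the dose is given. Mark it in the pregnancy-test row of section 8.3.17 at visits 8, 14 and 22. If the test is positive, withhold the dose and apply the Table 5 rule.

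The cost is three kits and three urine samples per woman of childbearing potential, plus a short amendment. No visit is added: these three visits already take place, with planned blood draws of 5, 5 and 31 mL. An occasional false positive would need a repeat test and could delay a dose. The change narrows the gap but does not close it, since a very recent conception can still test negative.

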8.3.13 Analysis of transmission reducing activity

Samples for SMFA will be collected from all subjects. Sera and/or purified IgG prepared from each serum will be used in the SMFA. Samples will be frozen until SMFA is planned. SMFA assays will be performed at Radboudumc (The Netherlands), using a qualified

standard membrane feeding assays using serum from subjects in cultures with *P. falciparum* and *Anopheles stephensi* mosquitoes.

8.3.14 Immunological assays: ELISAs/ PBMCs collection

Blood samples will be taken for isolation of peripheral blood mononuclear cells (PBMCs) and serum (see chart 8.3.17). PBMCs and sera will be frozen and can then be used by the Radboudumc or its collaborators for exploratory immunological assays to further analyse functionality of the immune response during and after R0.6C vaccinations. An ELISA assay will be used to measure circulating anti-R0.6C antibody titres in the subjects' sera at XX time points as shown in section 8.3.17, (sub)class and functionality (e.g. complement binding) may also be determined. In order to assess (antigen specific) T cell responses, the HLA-type of volunteers may be determined.

Samples that are not used in aforementioned immunological and functional assays will be stored up to 15 years and may be used for future (immunological) research relevant in the field of malaria vaccination.

8.3.15 Case report forms and data collection

All data collected by the investigators is registered in electronic case report forms. The investigator's notes are collected per subject in the coded trial EPD and are considered source data. Since all subjects will be healthy, there is no personal medical file for the study subjects, with exception of the medical file in case of adverse events/reactions resulting in a medical consultation or hospitalization. In this case the medical file will also be considered as source data. The diaries, produced by the study volunteers are also considered source data and will be kept as source documents.

8.3.16 COVID-19 related measures

With regards to the COVID-19 pandemic, the current Radboudumc guidelines will be followed. During the study period subjects will be instructed to call the trial physicians at any time if they experience severe symptoms or symptoms possibly related to COVID-19. SARS-CoV2 testing will be performed in accordance with current Radboudumc-wide guidelines. Follow-up visits not requiring blood collection for safety endpoints may be carried out by telephone, or at home, instead of at the clinical research center for subjects with suspected or confirmed SARS-CoV2 infection, until such time as they are considered no longer (potentially) contagious in accordance with current Radboudumc-wide guidelines. Vaccinations against the novel coronavirus SARS-CoV2 should preferably not take place within 30 days prior to or 14 days after each R0.6C vaccination.

8.3.17 Schedule of trial visits and measurements

Study Day ¹	I-120 to I1-1	I1-1	I1	I1+1	I1+2	I1+7	I1+14	I2-1	I2	I2+1	I2+2	I2+7	I2+14	I3-1	I3	I3+1	I3+2	I3+7	I3+14	I3+28	I3+56	I4-1	I4	I4+1	I4+2	I4+7	I4+14	I4+28	I4+56	I4+84
Days after first R0.6C administration	N/A	N/A	0	1	2	7	14	27	28	29	30	35	42	55	56	57	58	63	70	84	112	167	168	169	170	175	182	196	224	252
Visit No.	1	2	3	4	5	6	7	8	9	10	11	12	13	14	15	16	17	18	19	20	21	22	23	24	25	26	27	28	29	30
Informed consent	•																													
Inclusion/exclusion criteria	•	•																												
Demographic data and medical history	•																													
Physical examination ²	• ²	• ²	• ²	• ²	• ²	• ²	• ²	• ²	• ²	• ²	• ²	• ²	• ²	• ²	• ²	• ²	• ²	• ²	• ²	• ²	• ²	• ²	• ²	• ²	• ²	• ²	• ²			
Height and weight measurement	• ²																													
Blood pressure, temperature, pulse ³	•	• ³																												
Record concomitant medication	•	•	•	•	•	•	•	•	•	•	•	•	•	•	•	•	•	•	•	•	•	•	•	•	•	•	•	•	•	
HIV, HBV, HCV	•																													
Pregnancy test (urine)	•	•																												
Drugs screening (urine)	•	•																												

Study Day ¹	I-120 to I1 -1	I1-1	I1	I1+1	I1+2	I1+7	I1+14	I2-1	I2	I2+1	I2+2	I2+7	I2+14	I3-1	I3	I3+1	I3+2	I3+7	I3+14	I3+28	I3+56	I4-1	I4	I4+1	I4+2	I4+7	I4+14	I4+28	I4+56	I4+84
Distribution of emergency card		•																												
Distribution of diary		•																												
R0.6C administration			•						•							•								•						
Solicited local AEs (days 0-7)			•	•	•	•	•			•	•	•	•			•	•	•	•					•	•	•	•			
Solicited general AEs (days 0-14)			•	•	•	•	•	•		•	•	•	•			•	•	•	•	•			•	•	•	•	•			
Unsolicited AEs (days 0-84)		•	•	•	•	•	•	•	•	•	•	•	•			•	•	•	•	•	•		•	•	•	•	•	•	•	
Complete blood count ⁴	•	•		•	•	•	•	•		•	•	•	•			•	•	•	•	•			•	•	•	•	•	•	•	
Biochemistry tests ⁵	•	•		•	•	•	•	•		•	•	•	•			•	•	•	•	•			•	•	•	•	•	•	•	
PBMC isolations and citrate plasma		•																											•	
Serology/ELISA		•						•															• ⁷	•				•	• ⁷	•
SMFA ⁸		•						•															•		•			•		•
Safety Report ⁹							• ⁸																						• ⁸	
End of study visit																														•
Daily blood volume (ml)	12	63	0	5	5	5	31	5	0	5	5	5	15	5	0	5	5	5	31	5	4	31	0	5	5	5	47	5	4	31
Cumulative blood volume (ml)	12	75	75	80	85	90	121	126	126	131	136	141	156	161	161	166	171	176	207	212	216	247	247	252	257	262	309	314	318	349

1. Study days are represented as relative to the immunisation day. If an immunisation day takes place on a different day (+/-3 days is allowed for immunisation 2 and 3, +/-7 days is allowed for immunisation 4) the study visits related to that immunisation will shift accordingly. Moreover, following any given immunisation, for visits I#+7, I#+14 and I#+28 a relative window of +/-2 days is

allowed, for visits I#+56 and I#+84, a relative window of +/-10 days is allowed.

2. A physical examination including height and weight and vital parameters will be performed at the screening visit. On other visits, measurements may take place at the discretion of the physician.
3. Vital signs including body temperature, blood pressure and pulse will be recorded at the screening and inclusion visit. On other visits, measurements may take place at the discretion of the physician.
4. CBC test includes: hemoglobin, hematocrit, platelets, red blood cell count, MCV, white blood cell count + differentiation
5. Biochemistry test includes: creatinine, urea, sodium, potassium, bilirubin, AF, yGT, AST, ALT and LDH. Additional at screening: serology malaria (2mL), cholesterol, triglyceride and glucose (2mL).
6. For PBMC isolations and citrate plasma collection, timepoints I2+14, I4-1 and I4+84 are optional.
7. For serum samples collected at timepoints I3+56 and I4+56, +/-10 days is allowed.
8. SMFA assays will be performed with serum collected on minimally 3 time points (I1-1, I3+14 and I4+14). SMFA assays for other timepoints may not be performed if the results of I3+14 and I4+14 do not show significant transmission reduction compared to baseline (I1-1).
9. Safety report: A safety report will be prepared by the clinical investigator before initiation of a next group (2, 3 and 4), minimally 7 days after the first R0.6C administration in the preceding group. A safety report of all the safety data is made after the last study visit of group 4.

